- light walking around chair or in a circle: 3 circles

Stretches in standing position (with or without a chair) (≈ 15 min)

- a variety of lower-extremity muscle stretching and flexibility exercises that include:
 - quadriceps (thigh) stretch, hamstring stretch, calf stretch, ankle pivoting, circling, and stretch
- light walking around chair or in a circle: 3 circles

Stretches in chair (≈ 10 min)

- a variety of lower-extremity muscle stretching and flexibility exercises that include:
 - quadriceps (thigh) stretch, hamstring stretch, calf stretch, ankle pivoting, circling, and stretch

Stretches while moving around (≈ 8 min)

• a variety of upper- and lower-extremity and trunk stretching exercises in standing position, which may involve slow bending (forward, sideways), reaching (arm forward or upward, or sideways), and turning (one half-circle – 180 degrees)

Instructions: pay attention to the following:

- range of motion (ROM): slow progression from 50% to 80%-90% ROM
- repetitions: 3 reps of each stretch and held to the point of mild tension for 5 seconds
- rotation: if an exercise involves a rotation, repeat 3 times on each side
- circle: if an exercise involves circling (e.g., ankle), repeat 3 times
- · breathe naturally throughout the stretch

Winding-down (≈ 2 min)

• Seated or standing: light breathing and relaxing (meditative, verbal cued whole body) exercises - may repeat some of the warm-up exercises

Adverse events monitoring

Throughout the study period, both intervention- and non-intervention-related adverse events will be closely monitored and recorded by research staff and adjudicated by the Principal Investigator of the study. We will classify adverse events in three categories: Mild, Moderate, and Serious. Similarly, for all events observed or reported in this study, we will further classify them into three categories in relation to the intervention: Unrelated, Possible, or Definite. The following section describes the classification and categorization of our study adverse events. Per our IRB protocol, any serious adverse events will be reported to the IRB and the project Safety Officer within 48 hours of the reported incident.

Adverse Event and Serious Adverse Event Collection Process

The project defines Adverse Events and Serious Adverse Events as follows:

Definition of Adverse Events may include the following:

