- Any musculoskeletal pain or discomfort, including lower back pain, ankle/muscle soreness or pain, or a fall without needing medical attention
- Any event that requires medical treatment but is not an immediate life-threatening condition (e.g., eye surgery or a medical procedure)

Definition of Serious Adverse Events are undesirable experiences associated with the prescribed exercise interventions in this project. Serious Adverse Events may include the following:

- Death
- Falls that result in a serious injury that requires immediate medical attention
- Prolonged hospitalization
- Important medical or life-threatening events such as a heart attack that require treatment in an emergency room
- Events that cause persistent or significant disability or incapacity

Classification of Adverse Events

This project will classify any adverse events observed during the 6-month active exercise intervention period into the following three categories:

- Mild: events that require no medical treatment or are non-life threatening
- Moderate: events that require medical treatment but are not immediate life-threatening conditions
- Serious: events that result in death or are life threatening and require medical treatment, including prolonged hospitalization or significant disability/incapacity

Relatedness

For all events observed or reported, the project will further classify them into three categories in relation to the intervention:

- Not related: an event that is reported but not directly related to participation in the intervention
- Possibly related: an event that is observed during an exercise class that is considered likely to be associated with participation
- Definitely related: an event that is observed or reported during an exercise class and is considered directly related to participation.

Adverse Events and Serious Adverse Event (SAE) Reporting Process

We will carefully monitor for unexpected adverse events, as well as the expected outcomes, that participants experience during each online exercise session and outcome assessment, whether or not the events or outcomes are directly related to the study intervention. All symptoms reported by the study participants will be tabulated in a checklist format and recorded by a designated research assistant. When an adverse event is identified, the staff member will report it directly to the Principal Investigator (PI). An Adverse Event Report Form will immediately be completed, filed, and reported to PI.

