Throughout the study period, both intervention- and non-intervention-related adverse events will be closely monitored and recorded by research staff and adjudicated by the Principal Investigator. We will classify adverse events in three categories: Mild (i.e., events that require no medical treatment or are not life threatening), Moderate (i.e., events that require medical treatment but are not immediate life-threatening conditions), and Serious (i.e., events that result in death or are life threatening and require medical treatment, including hospitalization, or significant disability/incapacity). For all events observed or reported, we will further classify them into three categories in relation to the intervention: Unrelated (an event that is reported but not directly related to participation in the intervention), Possible (an event that is observed during a class and that is considered likely to be associated with participation), or Definite (an event that is observed or reported during a class and is considered directly related to participation).

Per our IRB protocol, any serious adverse events that we have collected during the entire course of intervention will be reported to the IRB and the project Safety Officer within 48 hours of the reported incident. This will also include unanticipated issues such as prolonged hospitalizations and deaths. Safety analysis will involve tabulating the occurrence of adverse events, including Serious adverse events (deaths and hospitalizations) and unanticipated problems/issues among the three groups. Given the low risk of the trial, no inferential statistical tests are planned for safety.

Statistical software

Statistical analyses will be performed with the use of Stata software (version 17, Stata Corp), SPSS software (version 25, SPSS), and Mplus software (version 8.4, Muthén & Muthén).

Programming plan

All statistical programs used to generate the study results and unidentifiable data will made available upon reasonable request to the PI of this project.

Data Management

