Throughout the study period, both intervention- and non-intervention-related adverse events will be closely monitored and recorded by research staff and adjudicated by the Principal Investigator. We will classify adverse events in three categories: Mild (i.e., events that require no medical treatment or are not life threatening), Moderate (i.e., events that require medical treatment but are not immediate life-threatening conditions), and Serious (i.e., events that result in death or are life threatening and require medical treatment, including hospitalization, or significant disability/incapacity). For all events observed or reported, we will further classify them into three categories in relation to the intervention: Unrelated (an event that is reported but not directly related to participation in the intervention), Possible (an event that is observed during a class and that is considered likely to be associated with participation), or Definite (an event that is observed or reported during a class and is considered directly related to participation).

Per our IRB protocol, any serious adverse events that we have collected during the entire course of intervention will be reported to the IRB and the project Safety Officer within 48 hours of the reported incident. This will also include unanticipated issues such as prolonged hospitalizations and deaths. Safety analysis will involve tabulating the occurrence of adverse events, including Serious adverse events (deaths and hospitalizations) and unanticipated problems/issues among the three groups. Given the low risk of the trial, no inferential statistical tests are planned for safety.

Statistical software

Statistical analyses will be performed with the use of Stata software (version 17, Stata Corp), SPSS software (version 25, SPSS), and Mplus software (version 8.4, Muthén & Muthén).

Programming plan

All statistical programs used to generate the study results and unidentifiable data will made available upon reasonable request to the PI of this project.

Data Management

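### The adverse event grades overlap: Mild as worded also covers treated events that are Moderate, and the Serious grade does not match the Serious Adverse Event list

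*Protocol*

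**What the plan says.** Protocol, Adverse events monitoring, sets up the scale: "We will classify adverse events in three categories: Mild, Moderate, and Serious". Classification of Adverse Events then defines the grades:

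- The lowest grade is worded as "Mild: events that require no medical treatment or are non-life threatening".
- For the middle grade the text is "Moderate: events that require medical treatment but are not immediate life-threatening conditions".
- At the top of the scale it has "Serious: events that result in death or are life threatening and require medical treatment, including prolonged hospitalization or significant disability/incapacity".

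Just before this, Adverse Event and Serious Adverse Event Collection Process gives two lists of its own. The adverse event list includes "Any event that requires medical treatment but is not an immediate life-threatening condition (e.g., eye surgery or a medical procedure". The Serious Adverse Event list, which is limited to experiences associated with the exercise interventions, includes "Falls that result in a serious injury that requires immediate medical attention" and attaches no life-threat condition to that item.

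The section Intervention safety and analysis, in the Protocol's statistical section and again in the stand-alone SAP, restates the grades. Mild keeps the *or*: "Mild (i.e., events that require no medical treatment or are not life threatening". Serious changes slightly: "Serious (i.e., events that result in death or are life threatening and require medical treatment, including hospitalization, or significant disability/incapacity". The word *prolonged* is gone.

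The same section has the Principal Investigator adjudicate events, plans a tabulation of events among the three groups, glosses Serious events in that tabulation as deaths and hospital admissions, and rules out inferential safety tests. Neither document says that the grades are exclusive, that the highest grade applies, or how to break a tie.

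**The concern.** A severity scale should give each event one grade. Here the definition of Mild is met by either of two conditions, and the second (not life threatening) is also true of most events that the next grade is meant to hold. At the upper end there are two tests of seriousness. One is a list that includes injurious falls; the other is a grade that turns on death or life threat. They disagree on some falls, a foreseeable event in a trial of stepping and balance exercise in people aged 65 or older.

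Because safety is reported only descriptively, the counts are the safety result. If two people applying the text faithfully can put the same event in different grades, the number of Serious events in an arm depends on an unwritten choice. Where serious events are few, moving one or two could change how the arms compare.

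**Working it through.** No sample size, power or event count bears on this point, so the check sets the definitions side by side as logic.

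Let T = requires medical treatment, L = life threatening, and I = immediately life threatening (I implies L). Taken literally:

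- Mild = (not T) or (not L)
- Moderate = T and (not I)
- Serious grade = death, or (L and T), or prolonged hospitalization or disability if the *including* clause is read as sufficient on its own
- Serious by list = on the Serious Adverse Event list, including the injurious fall

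| Event | As written | With *and* in Mild |
|---|---|---|
| (a) Untreated, not life threatening | Mild | Mild |
| (b) Untreated, life threatening | Mild | no grade |
| (c) Treated, not life threatening, not on the list (e.g. eye surgery) | Mild and Moderate | Moderate |
| (d) Treated, not life threatening, fall with serious injury on the list | Mild and Moderate by grade, Serious by list | Moderate by grade, Serious by list |
| (e) Treated, not life threatening, prolonged hospitalization or disability | Mild and Moderate, plus Serious if the *including* clause suffices | Moderate, plus Serious on the same condition |
| (f) Treated, life threatening but not immediately so | Moderate and Serious | Moderate and Serious |
| (g) Treated, immediately life threatening | Serious | Serious |

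Four results follow.

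1. *Lower boundary.* Rows (c) to (e) meet both Mild and Moderate. Row (f) is Moderate but not Mild; it overlaps Serious instead. On the literal text, every event that meets Moderate also meets at least one other grade.
2. *Upper boundary.* Row (d) is the real conflict between list and grade. Changing *or* to *and* removes Mild from it and leaves Moderate against Serious unresolved.
3. *Hospitalization wording.* A short admission that is neither life threatening nor disabling falls outside the clause in Classification of Adverse Events (prolonged stays) but inside the one in Intervention safety and analysis (any stay). The gloss in the tabulation sentence is different again: an injurious fall treated without admission is on the Serious list but is neither a death nor an admission, so it could be left out of the serious count.
4. *Limit of the one-word change.* Row (b) is Mild now and would have no grade under *and*. It may be rare, but the reconciled Serious definition has to cover it.

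**The case against.** The best reply is that this is a drafting slip whose intent is plain. The treated-event item in the adverse event list is nearly the Moderate definition and carries the eye-surgery example, while the item before it covers falls that need no medical attention. A sensible adjudicator would treat the grades as an ordered scale and give each event one grade. That is a fair account of Mild against Moderate, but it supplies no rule for the injurious fall, where list and grade disagree however Mild is read.

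There are also several stronger readings that a reader might infer and that the documents do not support.

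- *Every Moderate event is also Mild.* This needs *not life threatening* and *not immediately life threatening* to mean the same. If they differ, row (f) is an exception.
- *A fracture graded Moderate escapes expedited reporting.* In the Protocol's Adverse Events and Serious Adverse Event (SAE) Reporting Process, expedited reporting covers Serious Adverse Events, which are defined by the list and not by the grade. The same section sends each recorded event to the IRB, Safety Officer and Project Officer within 3 working days. Adverse Events Reporting, in both documents, gives 48 hours to the IRB administrator and Safety Officer with no severity condition. Only the separate 48-hour statement in Adverse events monitoring and in Intervention safety and analysis is tied to seriousness.
- *A planned severity-by-arm table is undefined.* No such table is named. The plan has a three-grade classification and a tabulation of events by group. Totals and deaths do not depend on the line between Mild and Moderate.
- *An unmasked person does the grading.* The Principal Investigator adjudicates and is not among those listed as masked in the synopsis, but no section states the adjudicator's masking status.

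Finally, the Serious list is limited to intervention-associated events, so an unrelated fall does not raise the conflict with the list.

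**Conclusion.** The point holds, and it is minor. As written, the grades are not mutually exclusive. Treated, non-life-threatening events meet both Mild and Moderate. An intervention-associated fall with serious injury, urgently treated but not life threatening and without a prolonged stay or disability, is Serious by the list and Moderate (literally also Mild) by grade. The Serious definition is also inconsistent on hospitalization between sections.

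The consequence is confined to how safety events are labelled and counted by group. Efficacy inference is untouched, and prompt reporting is largely protected. The documents give no expected or observed event numbers, so how many events would change grade cannot be stated.

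The conclusion rests on a literal reading of the definitions and on the absence of any precedence rule. For row (e) it also depends on how the *including* clause is read.

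**What to change.** 1. In Classification of Adverse Events (Protocol) and in Intervention safety and analysis (Protocol and SAP), change *or* to *and* in the definition of Mild.
2. Reconcile the Serious grade, the Serious Adverse Event list, the two hospitalization wordings and the gloss in the tabulation sentence, so that each event has exactly one grade. The reconciled text should settle the injurious fall, say whether *life threatening* and *immediate life-threatening* differ, and leave no event without a grade (row (b)).
3. Recheck the events in the Adverse Event Log against the reconciled rule for any safety table still to be produced. Both documents cite a trial report from October 2023, so for tables already reported, state which rule was used.

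The cost is a few words in three places, one reconciled definition, and a single pass through a log that already holds a description of each event. No new data are needed.

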The PI will be directly responsible for monitoring and documentation of adverse events during the implementation of all prescribed exercise sessions across the three study conditions. Once the project is implemented, any activities (during a class session or during an assessment session) resulting in participant distress or discomfort, exercise-related side effects, injuries, or falls will be reported immediately to the PI, who will, upon consultation with other members of the team, take appropriate action. This will include consultation with the team's medical expert. The PI will report such incidents immediately to the IRB Chair at ORI. Summary reports of adverse events, and any subsequent IRB action taken as a result of such events, will be routinely provided to the NIA PO and the NIA-appointed Safety Officer.

For each event observed or reported, regardless of setting where the event takes place (i.e., at home or during exercise classes), a designated research assistant will contact the participant within 3 working days, via a telephone call, to ascertain detailed information related to the event. During this phone contact, information about date/time, location, nature of the event, symptoms experienced, and any measures taken for the event will be collected and documented. If necessary, the informant for the study participant will be contacted to verify the information provided by the participant. The recorded event, along with a detailed description, will be tabulated in a checklist format and entered into the project's Adverse Event Log. It will be shared immediately with the PI, who will report, within 3 working days, to the IRB, NIA-appointed Safety Officer, and Project Officer at NIA.

The following summarizes the reporting procedure to be implemented in this project:

- Expedited reporting: All SAEs (including expected and related or possibly related) observed during the active study period will be reported to local IRB and Safety Officer within 3 working days.
 - Routine reporting: All events will be included in routine reports.

Fidelity of intervention delivery

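### The possibly related category admits only adverse events observed in class, so a plausible but not direct out-of-class harm can only be labelled not related, and a directly related one reported outside class fits no category

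*Protocol*

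**What the plan says.** The Relatedness section of the Protocol gives every event, whether staff saw it or only heard of it, one of three labels. The middle label, for a possible link, is reserved for "an event that is observed during an exercise class that is considered likely to be associated with participation". The strongest label has a wider setting condition, since hearing of the event in a session is enough; it covers "an event that is observed or reported during an exercise class and is considered directly related to participation". The remaining label, for unrelated events, has no setting condition at all and takes in "an event that is reported but not directly related to participation in the intervention".

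The scheme appears twice more, under Intervention safety and analysis in the Protocol's statistical section and under the same heading in the SAP. Both of these define the middle category as "an event that is observed during a class and that is considered likely to be associated with participation".

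What is collected is much wider. The Protocol's definition of adverse events includes "Any musculoskeletal pain or discomfort, including lower back pain, ankle/muscle soreness or pain, or a fall without needing medical attention", with no requirement that the event arise in class. The SAE Reporting Process section has staff telephone the participant about each event, "regardless of setting where the event takes place (i.e., at home or during exercise classes"), and record its date and time, location and nature. It adds that "All events will be included in routine reports". The Annual Progress Reports section lists information on intervention-related and non-intervention-related adverse events among the items sent to the IRB and the Safety Officer.

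**The concern.** A relatedness category should express how likely it is that the intervention caused the event. Here two of the three categories also depend on where staff saw or heard of it, and the less certain category carries the stricter condition. Soreness mentioned at the next class can be definite but cannot be possible. The same soreness reported by telephone, which the Adverse Events Reporting section encourages, can be neither.

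At stake is the split between related and unrelated events. It is a reported safety output through the annual reports, and no inferential safety tests are planned, so readers depend on descriptive classification. Under the modified protocol, participants exercise at home over videoconference and the definitions are not changed, so observation during a class remains the test.

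**Working it through.** No arithmetic applies: the documents state no adverse-event rate and no share of events arising outside class. The check is to run each combination of setting and judged causal link through the three definitions. Inputs are the definitions in the Protocol's Relatedness section (the other two copies agree on the setting conditions) and the rule that every event receives one of the three labels.

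| How staff learn of the event | Directly related | Plausible or likely, not direct | No link |
|---|---|---|---|
| Observed during a class | Definite | Possible | Not related |
| Not observed in class, reported during a later class | Definite | Not related | Not related |
| Not observed in class, reported outside class (e.g. by telephone) | No category | Not related | Not related |

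1. **First row.** The scheme works as intended. The wording of not related excludes only direct links, so it overlaps with possible here. I take possible to prevail, as the more specific definition.
2. **Second row.** A directly related event qualifies as definite, because that definition accepts events reported in class. A plausible but not direct one fails possible, because it was not observed in class, and fails definite, because the link is not direct. It literally meets not related.
3. **Third row.** A plausible but not direct event again meets only not related. A directly related event fails possible and definite on setting and fails not related on causality, so no label fits.

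Four cells combine some causal link with an event not observed in class. Two go to not related, one to no category and one to definite: 2 + 1 + 1 = 4. In no cell does a setting condition turn an unrelated event into a related one. The literal rule can take events out of the related categories but cannot add any.

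**The case against.** The strongest reply is that safety oversight does not rest on this label. Events in any setting are followed up and logged, all enter routine reports, and expedited reporting is written to cover all serious events. The planned safety analysis tabulates adverse events among the three groups without restricting them to related ones and specifies no table by relatedness. The Principal Investigator adjudicates and may in practice judge more broadly than the wording allows. Most of this stands: it confines the problem to the relatedness breakdown. Adjudication does not remove it, because these definitions are the only written criteria the adjudicator has.

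A reader might also infer more than the documents support:

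- **That all delayed soreness and later falls are forced into not related.** They are not. Classes run twice weekly, and an event reported at the next one and judged directly related is definite. One reported elsewhere and judged directly related is unclassifiable, which is a different fault.
- **That nearly all related events are lost because classes occupy so little of the week.** Two 60-minute sessions are 2 of 168 hours, or 1.2%. That is a share of time, not of events, and exercise-related events need not be spread evenly over the week.
- **That the undercount falls mainly on the tai ji quan arms.** Planned intensity is higher there than in the stretching arm, but the documents give no harm rates by arm and no timing of events by arm. A differential effect is conjecture.

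**Conclusion.** The point holds as a defect in the written definitions. The possible category excludes every event not observed in class, contrary to the plan's own all-settings capture, and the definite category leaves a gap for directly related events reported outside class. The gap in wording is certain. The direction of any error, towards too few related events, follows if the definitions are applied literally and the causal judgements are otherwise sound. Its size cannot be computed from the documents and may be small. Total adverse-event counts by arm and the efficacy analyses are untouched. The change should be made because a reported safety classification is incoherent as written and errs in the reassuring direction; nothing here shows that the trial's overall safety picture is wrong.

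**What to change.** - Delete the in-class conditions from the possible and definite categories in all three places: the Protocol's Relatedness section, Intervention safety and analysis in the Protocol, and the same heading in the SAP.
- State that relatedness is judged on timing and mechanism, regardless of where the event occurred or was reported. At the same time, word not related so that it no longer overlaps with possible.
- Re-adjudicate events already logged. The modified protocol describes conduct in the past tense, so rewording alone would not correct labels already assigned. The follow-up call already records date and time, location and nature, so no new data field is needed.
- If relatedness was in practice judged more broadly than the text allows, state the rule that was used.

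The cost is a few words per definition and some re-adjudication work. Related-event counts may be slightly less favourable.
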